8.2.2 Severity Assessment

AEs occurring during this study will be graded in accordance with the NCI CTCAE Version 4.03. Documentation of AE grading in the source documents and CRF should be consistent with provided definitions.

8.2.3 Causality

For each AE, the investigator should determine and document whether there exists a reasonable possibility that the study treatment caused or contributed to the AE. The investigator's assessment should be recorded in the source document. The CRF will provide the options for attribution to study treatment as "related" and "not related." If the investigator's causality assessment is "unknown but not related to investigational product," this should be recorded in the CRF as "not related." If the investigator does not know whether or not the study treatment is causally-related to the event, reporting for study purposes will be as "related" to study treatment.

Collection of causal relationship for AEs associated with study procedures (e.g., tumor biopsy) is provided for separately in the CRF.

8.3 Serious Adverse Events

8.3.1 Definition of a Serious Adverse Events

An SAE is any event that meets any of the following criteria:

- Results in death;
- Is life-threatening (immediate risk of death);
- Requires inpatient hospitalization or prolongation of existing hospitalization;
- Results in persistent or significant disability/permanent damage (substantial disruption of the ability to conduct normal life functions);
- Results in congenital anomaly/birth defect.
- Other: Important medical events that may not result in death, be life-threatening, or require hospitalization, may be considered an SAE when, based upon appropriate medical judgment, they may jeopardize the patient and may require medical or surgical intervention to prevent one of the outcomes listed in this definition. Examples of such events are:
 - Intensive treatment in an emergency room or at home for allergic bronchospasm
 - Blood dyscrasias or convulsions that do not result in inpatient hospitalization
 - Development of drug dependency or drug abuse

Progression of the malignancy under study, including any signs or symptoms of progression that may require hospitalization, should not be reported as an SAE unless the outcome is fatal within the safety reporting period.

Definition of Terms

Life threatening: An AE is life threatening if the patient was at immediate risk of death from the event as it occurred; i.e., it does not include a reaction that if it had occurred in a more serious form might have caused death. For example, drug-induced hepatitis that resolved without evidence of hepatic failure would not be considered life-threatening even though drug-induced hepatitis can be fatal.

Hospitalization: Hospitalization for elective surgery or routine clinical procedures that are not the result of AE (e.g., elective surgery for a pre-existing condition that has not

worsened) need not be considered AEs or SAEs. If anything untoward is reported during the procedure, that occurrence must be reported as an AE, either 'serious' or 'non-serious' according to the usual criteria.

In general, hospitalization signifies that the patient has been detained (usually involving at least an overnight stay) at the hospital or emergency ward for observation and/or treatment that would not have been appropriate in the physician's office or outpatient setting. When in doubt as to whether 'hospitalization' occurred or was necessary, the AE should be considered serious.

Disability/permanent damage: An AE is disabling or caused permanent damage if it resulted in a substantial disruption of a person's ability to conduct normal life functions, e.g., a significant, persistent or permanent change, impairment, damage or disruption in body function/structure, physical activities and/or quality of life.

8.3.2 Exposure During Pregnancy

Exposure during pregnancy (i.e., exposure in-utero [EIU]) may occur in a female study participant, the female partner of a male study participant or study site personnel working with the investigational product (e.g., occupational exposure) if:

- A female becomes or is found to be pregnant during treatment or within 6 months after discontinuing treatment or having been directly exposed to the investigational product;
- A male is exposed to the investigational product prior to or around the time of conception or during the pregnancy of his partner.

If exposure in-utero occurs, the investigator must submit an SAE form and an EIU Supplemental Form within 24 hours of awareness of the exposure, regardless of whether an AE or SAE has occurred.

In the event of pregnancy in a female study participant, if the pregnancy is continued, study treatment will be immediately discontinued.

In the event of exposure of the pregnant partner of a male study participant, the study participant should be asked to deliver an EIU Pregnant Partner Release of Information Form to his partner. The Investigator must document on the EIU Form that the patient was given this letter to provide to his partner.

Follow-up to obtain pregnancy outcome information is to be conducted for all EIU reports. In the case of a live birth, the health of the neonate should be assessed at the time of birth and for up to 3 months after birth. Further follow-up of birth outcomes will be handled on a case-by-case basis (e.g., follow-up on preterm infants to identify developmental delays). In the event the pregnancy is terminated, the reason(s) for

termination should be reported and, if clinically possible, the structural integrity of the terminated fetus should be assessed by gross visual inspection.

If the outcome of the pregnancy meets the criteria for an SAE (i.e., ectopic pregnancy, spontaneous abortion, intrauterine fetal demise, neonatal death, or congenital anomaly), an SAE report should be submitted to the Sponsor.

8.4 Reporting of SAEs and AEs

8.4.1 Reporting Period

The active reporting period for SAEs begins from the time that the patient provides main study informed consent (i.e., prior to undergoing any study-specific procedure or assessment) and continues until all SAEs have resolved or stabilized to a chronic condition, whichever is later. Death must be reported if it occurs during the active reporting period for SAEs regardless of whether a subsequent anticancer therapy is administered. Serious adverse events occurring to a patient after the active reporting period has ended should be reported to the Sponsor if the investigator becomes aware of them and if the investigator assesses at least a reasonable possibility of being related to study drug.

The reporting period for non-serious AEs begins from the day of first dose of study treatment and continues until at least 28 days after last administration of study treatment and/or until recovery from all acute toxicities associated with the drug administration to a chronic condition, whichever is later. If a patient begins a subsequent anticancer therapy, the AE reporting period ends at the time the new treatment is started.

8.4.2 Reporting Requirements

All SAEs must be reported within 24 hours of Investigator/site knowledge of the event, irrespective of the extent of available AE information, by faxing the SAE report to the Sponsor's pharmacovigilance representative designated in the Study Manual. The 24-hour timeframe also applies to additional new information (follow-up) on previously forwarded SAE reports and to the initial and follow-up reporting of exposure during pregnancy and exposure via breastfeeding. The need for an expedited report to regulatory authorities will be determined by the Sponsor and necessary reporting will be performed by the Sponsor. The Sponsor will notify study investigators of all Suspected, Unexpected (as judged against the Investigator Brochure) Serious Adverse Reaction (SUSAR) reports. The investigator is responsible for reporting all SUSARs to the IRB/EC.

All AE (including SAEs) must be documented in source documents and reported in the CRF. Please note that the CRF and SAE report forms may collect information in somewhat different formats. Where the requested data overlap in different formats, the information should be consistent between the two forms.

9 STATISTICS

Detailed methodology for summary and statistical analyses of the data collected in this study will be documented in a Statistical Analysis Plan (SAP), which will be maintained by the Sponsor. The SAP may modify the plans outlined in the protocol; however, any major modifications of the primary endpoint definition and/or its analysis will also be reflected in a protocol amendment.

9.1 Hypothesis and Sample Size

This Phase 2, parallel-arm study will use a Bayesian Predictive Probability Design (Lee-2008) that minimizes the number of patients enrolled to test the hypothesis. The design will be applied separately and using the same assumptions in each of four treatment arms. As many as 45 patients are planned for inclusion in the primary analysis for each treatment arm. The study also provides for the addition of up to 55 patients to each of two treatment arms to provide sufficient safety and/or efficacy data to support an accelerated approval market application in two study populations. Thus, the ultimate sample size for this study could include as many as 290 patients.

ORR in accordance with RECIST v1.1 is the primary endpoint. With currently available treatments, ORR is assumed to be 20% (p_0), thus this rate is considered uninteresting. The target ORR using MGCD265 in this study is 40% (p_1). The trial will monitor the number of observed responses continuously after evaluating the first on-study disease assessments of the first 10 patients in each treatment arm in the mITT population. In creating the statistical design, the Type 1 error (α) is constrained to < 0.05 and Power ($1-\beta$) is constrained to ≥ 0.90 .

Using the parameters identified, the ultimate sample size for each treatment arm is as many as 45 patients in the mITT population. The stopping rules (rejection regions), expressed as number of responses per patients treated, are 0/10, 1/14, 2/18, 3/22, 4/26, 5/29, 6/32, 7/35, 8/37, 9/39, 10/41, 11/43, 12/44, and 13/45. Thus, if more than 13 responses are observed among the first 45 patients enrolled who meet the criteria for the mITT population, the drug will be declared efficacious. If the true ORR is 20% (null hypothesis), the probability of early termination (under H_0) during the study is 0.92 and the expected sample size prior to termination is 28 patients. The Type 1 error is equal to 0.0499 and Power equal to 0.9065. If the true ORR is 40%, the probability of rejecting the hypothesis at each evaluation of the stopping rules varies, but cumulatively is 0.0935. If the true ORR is 40% and $N=45$, the exact 95% confidence interval (Clopper-Pearson) around the point estimate for ORR will be (25.7, 55.7). If the outcome in a treatment arm is promising and the option is taken to enroll up to 100 patients in the mITT in a specific treatment arm (45 patients in the initial arm plus 55 patients), to narrow the confidence interval around the ORR point estimate and to increase the size of the safety database, the exact 95% confidence interval around a true ORR of 40% will be (30.3, 50.3). Data collected in patients enrolled beyond the planned Phase 2 sample size will be used in secondary and supportive analyses. The primary analysis includes independent

evaluation of each of the four treatment arms in the first 45 patients; study expansion enables confirmation of the results of the primary analysis. The use of the Bayesian Predictive Probability Design within each arm effectively controls the overall Type I error to a maximum of 5% for each population of interest.

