Sponsor-approved local test, retrospective analysis by the central tissue testing laboratory is key.

Treatment Arms C and D, based on documentation of target gene alteration using the ctDNA test, are intended to include patients for whom central laboratory tumor tissue testing fails for technical reasons, or the search for suitable tumor tissue or test results prove that none exist (to be documented in the patient records).

Individual patients with gene alterations are likely to qualify for entry into two or more treatment arms. The correlation between target gene mutations in tumor tissue and ctDNA is expected to be high. In addition, patients may have both target gene mutation and amplification. The priority for assignment to treatment arm will be in the order A to D listed above.

The Phase 2 study will use a Bayesian Predictive Probability Design ([Lee-2008](#)), applied separately and using the same assumptions in each treatment arm (see Section 9.1). Emerging tumor response data will be evaluated continuously beginning after 10 patients in each treatment arm have completed their first on-study disease assessment and are considered part of the mITT population. Stopping rules for futility are described in Section 9.1. Assuming the stopping rules are not triggered, the total sample size to be evaluated in each treatment arm of the Phase 2 study is 45 patients. The primary analysis will be conducted in the mITT (defined in Section 9.3.1).

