9.3 Analysis Populations

9.3.1 Modified Intent-to-Treat Population

The Modified Intent-to-Treat (mITT) population is defined in each arm as all patients who receive treatment at least one dose of MGCD265 on this study.

The primary efficacy analyses of the primary and secondary efficacy endpoints will be performed in the mITT population.

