9.4 Efficacy Endpoint Definitions and Analyses

9.4.1 Objective Response Rate

Objective disease response will be categorized in accordance with RECIST v1.1 (Appendix 2). Objective Response Rate (ORR) is defined as the percent of patients documented to have a confirmed Complete Response (CR) or Partial Response (PR), as reported by the central review laboratory. The primary analysis will be conducted approximately 12 weeks after the last patient is enrolled, allowing for observation of an early disease response and confirmation of PR or CR. ORR as reported by the investigator in the CRF will be used in secondary and supportive analyses as well as by the Internal Data Monitoring Committee for purpose of decision making using the Bayesian Predictive Probability Design.

Descriptive statistics (frequency and percentage) for ORR, CR, and PR will be presented. The exact 95% confidence interval of these response rates will be constructed. An exact test for single proportion (two-sided $\alpha=5\%$) will be performed to test $H_0: ORR \leq 20\%$ against $H_1: ORR > 20\%$. Other details will be described in the SAP.

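### In an expanded arm, is the primary ORR analysis in the first 45 patients or in the whole mITT of up to 100?

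*Combined protocol and SAP*

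**What the plan says.** Three parts of the protocol bear on this.

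- **Section 9.1** plans up to 45 patients per arm for the primary analysis. It declares efficacy if more than 13 responses occur among the first 45 enrolled who qualify for the mITT. It describes the primary analysis as an independent "evaluation of each of the four treatment arms in the first 45 patients; study expansion enables confirmation of the results of the primary analysis". On later patients it says: "Data collected in patients enrolled beyond the planned Phase 2 sample size will be used in secondary and supportive analyses". It also allows the sponsor to "enroll up to 100 patients in the mITT in a specific treatment arm", which is 45 plus 55. The Study Summary repeats the success rule and the supportive role, and Section 3 gives 45 as the number to be evaluated per arm.
- **Section 9.3.1** says the mITT "is defined in each arm as all patients who receive treatment at least one dose of MGCD265 on this study", and "The primary efficacy analyses of the primary and secondary efficacy endpoints will be performed in the mITT population". It sets no limit of 45. Section 3 also places the primary analysis in the mITT and refers to this definition.
- **Section 9.4.1** gives an exact test of ORR ≤ 20% at two-sided 5%. On the interval it says: "The exact 95% confidence interval of these response rates will be constructed". It states no sample size. On timing: "The primary analysis will be conducted approximately 12 weeks after the last patient is enrolled". It leaves other details to the SAP.

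**The concern.** An analyst who goes straight to the population section finds an uncapped mITT, and 9.1 itself counts expansion patients as mITT members. Read literally, 9.3.1 gives a primary analysis of up to 100 patients in an expanded arm, whereas 9.1 gives 45. Section 9.4.1 does not help, because its last patient could be the 45th in the arm or the last one added in expansion.

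The two sets can give different answers. With 15/45 followed by 11/55, the first 45 are positive (exact 95% interval 20.00% to 48.95%), but the pooled 26/100 is not (17.74% to 35.73%). Expansion is meant to support an accelerated-approval application. If the set were truly open, it could be chosen after the expansion data were known.

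**Working it through.** **Inputs.** From Section 9.1: null ORR 20%, target 40%; stopping boundaries 0/10, 1/14, 2/18, 3/22, 4/26, 5/29, 6/32, 7/35, 8/37, 9/39, 10/41, 11/43, 12/44, 13/45; success at 14 or more of 45; expansion by 55. From Section 9.4.1: exact test, two-sided 5%.

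**Step 1: the plan's own figures.** Let f_n(x) be the probability of x responses in n patients with the arm still open. Then f_n(x) = (1−p)·f_{n−1}(x) + p·f_{n−1}(x−1), with f_n(x) set to 0 at each boundary n when x is at or below the boundary count. Success is the sum of f_45(x) over x ≥ 14.

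- p = 20%: success 0.0499 (stated 0.0499); early termination 0.920 (stated 0.92); expected N 28.3 (stated 28).
- p = 40%: success 0.9065 (stated 0.9065).

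The stated error rates therefore belong to the first-45 rule.

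**Step 2: the cut-off for 100 patients.** The 9.4.1 test is positive when the lower Clopper-Pearson limit exceeds 20%. At N = 100 this needs 29 responses (lower limit 20.36%, one-sided p 0.020); 28 gives p 0.034 and fails.

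**Step 3: how often the set changes the answer.** Assumptions, since the protocol states no numerical trigger: expansion only at 14/45 or better, 55 patients added, and the same reader at both looks. The chance of passing both is the sum over x ≥ 14 of f_45(x)·P(Bin(55, p) ≥ 29 − x).

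| True ORR | Passes 14/45 | Passes 14/45 and 29/100 | Difference, all arms | Difference, expanded arms |
|---|---|---|---|---|
| 20% | 0.0499 | 0.0098 | 0.040 | 80.3% |
| 25% | 0.2084 | 0.1148 | 0.094 | 44.9% |
| 30% | 0.4780 | 0.4073 | 0.071 | 14.8% |
| 35% | 0.7423 | 0.7226 | 0.020 | 2.7% |
| 40% | 0.9065 | 0.9043 | 0.002 | 0.2% |

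Every expanded arm has already passed at 45, so disagreement runs one way only: positive on 45, not positive on 100. Even if either set could be called primary, the false-positive rate under this rule would stay at 0.0499.

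**Step 4: why a larger disagreement can appear.** If the first 45 are scored by the 9.4.1 two-sided test, the cut-off is 15/45 (one-sided p 0.02499), because 14/45 gives p 0.052. At true ORR 30%, disagreement then reads 25.6% of expanded arms: 17.7% positive on 100 only and 7.8% positive on 45 only.

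Every arm in the 17.7% has exactly 14/45, which 9.1 already declares efficacious. Arms with exactly 14/45 make up 24.7% of expanded arms, so 24.7 − 17.7 = 7.0% fail at 100. Then 7.0 + 7.8 = 14.8%, the figure in the table. For example, 14/45 followed by 16/55 gives 30/100 (21.24% to 39.98%): success under 9.1 and positive on the pooled set, so no reversal.

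The same applies to power at true ORR 40%. Scoring at 15/45 gives 0.851 against 0.904 for the pooled set, but 9.1's own rule gives 0.9065. The gap comes from the 14 versus 15 cut-off, a separate matter from which patients are analysed.

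**The case for a change.** The best case for a change is that no sentence gives 9.1 precedence, that analysts take the analysis set from the population section, and that mITT cannot silently mean the first 45 when 9.1 itself speaks of 100 in it. Enrolment runs without a planned pause, so an arm could pass 45 even without formal expansion. Interim data are reviewed by sponsor representatives (Section 9.8), which argues for fixing the set in advance. At a true ORR of 20% to 25% the choice often matters once an arm has expanded. The first-45 estimate is also the more biased of the two after a pass: mean ORR given expansion is 35.7% against 32.5% pooled when the truth is 30%.

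The textual part stands only as a wording gap. The mITT definition says who qualifies; 9.1 then takes the first 45 who do. An analysis of those 45 is still in the mITT, so the general statement and the specific rule can both hold, and the rule also covers an arm that over-enrols. The set is thus fixed in advance, and an analyst who applies 9.1 modifies nothing.

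The bias is real, but it is the price of a primary test with the stated error rates. It shrinks to 41.3% against 40.6% at the target ORR. The pooled estimate, which expansion is meant to sharpen, remains available as a supportive result.

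**Conclusion.** The concern does not call for a change. The protocol fixes the primary ORR set at the first 45 mITT patients per arm and makes expansion patients supportive; 9.3.1 merely omits to repeat this, and 9.4.1 names no competing set. No stated figure is wrong.

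The unspecified last patient in 9.4.1 affects the data cut-off and the length of follow-up, not which 45 patients are counted. The SAP, to which 9.4.1 defers, can settle it.

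Under 9.1's own rule the choice of set would change the result in 14.8%, 2.7% and 0.2% of expanded arms at true ORR 30%, 35% and 40%. At 20% the share is 80.3%, but only 5.0% of such arms expand, so it concerns 4.0% of all arms. These figures rest on expansion at 14/45 or better, 55 added patients and one reader; in the plan, stopping uses the investigator's reading and the primary ORR the central one. Making the pooled set primary would trade less bias for a rule whose error rates the plan does not state, which is a matter of choice rather than a correction. The difference between success at 14/45 in 9.1 and the 15/45 needed by the test in 9.4.1 is a separate question, and restating the first-45 limit would not resolve it.

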9.2 Data Handling

Listings of all patient data will be prepared. Data summaries will be presented in tabular and/or graphical format and summarized descriptively, by the four groups of patients having genetic tumor alterations activating *MET*, where appropriate. If some (or all) of those four groups of patients show similar objective response rate, data summaries (efficacy and safety) will also be presented for those groups combined as supportive analyses. Response rates will be considered similar between groups, if they are within $\pm 10\%$. Further details of planned analyses will be described in the SAP.

For all variables, only the observed data from patients will be used in the statistical analyses; there is no plan to estimate missing data. Patients without a valid clinical response assessment will be assigned a best overall response of not evaluable (NE). Data from patients who are lost to follow-up or have missing observations before reaching an endpoint in any of the time-to-event analyses will be treated as censored with specific rules defined in the SAP.

9.3 Analysis Populations

9.3.1 Modified Intent-to-Treat Population

The Modified Intent-to-Treat (mITT) population is defined in each arm as all patients who receive treatment at least one dose of MGCD265 on this study.

The primary efficacy analyses of the primary and secondary efficacy endpoints will be performed in the mITT population.

